5.0 Study Outcomes

5.1 Primary Outcomes

- 5.1.1 Cardiac toxicity(see 2.2.3), as measured by MRI (ejection fraction [EF], left ventricular end diastolic volume [LVEDV], left ventricular end systolic volume [LVESV], T1/T2 mapping and myocardial strain) measures and ECHO (EF, myocardial strain, LVEDV, LVESV, ESV, mitral inflow E, A, E' and A') measures. Cardiac toxicity is defined as reduction in LVEF of $\geq 10\%$ compared to baseline LVEF and $EF \leq 50\%$ on the follow-up scan. This assessment will be performed using both an ECHO and MRI measure. In addition, the primary outcome will be assessed at the 3 month follow-up (or relapse) visit.
- 5.1.2 Other unexpected toxicities (exclude hematologic and infectious) \geq grade 3, as measured by CTCAE v 4.0
- 5.1.3 Feasibility, as measured by ability to administer continuous infusion daunorubicin and complete required study assessments with limited deviation from the proposed regimen (as defined in section 8.2)

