8.2 Definitions

- Study Regime: Completion of the critical study regime tasks will be tracked by research staff and recorded as “Yes” or “No” in Appendix E, The Cardiac Function form. The tasks that should be recorded in this manner are the following:
 - The daunorubicin infusion (Induction):
 - if this is not completed in 72 hours +/- 1, record as “No”,
 - If the infusion is completed within these parameters record “yes”.
 - If “No”, record the total infusion amount and time taken to administer.

**CYTARABINE PLUS CONTINUOUS INFUSION DAUNORUBICIN, WITH CARDIAC
MRI MONITORING, INDUCTION THERAPY FOR ADULTS WITH ACUTE MYELOID
LEUKEMIA; A FEASIBILITY STUDY**

Wake Forest Baptist Comprehensive Cancer Center (WFBCCC) CCCWFU 22616

- ECHO (at pre-induction visit, *post-treatment (pre-discharge), 3 month follow-up or relapse):
 - Record “Yes” or “No” if the patient completes or does not complete the ECHO at each visit.
 - *indicates an additional assessment for those individuals requiring a second cycle of Induction therapy
- MRI (at pre-induction visit, 3 month follow-up or relapse, at 6 month follow-up or relapse):
 - Record “Yes” or “No” if the patient completes or does not complete the MRI at each visit.
- Evaluable for toxicity: All patients will be evaluable for toxicity from the time of their first treatment with daunorubicin.
- Persistent leukemia: Patients not achieving a remission after 2 induction attempts; these patients will be removed from the study.
- Disease-free survival: calculated for patients who achieve CR and measured from the date of CR until relapse from CR or death. Observation is censored at the date of last follow-up for patients last known to be alive without report of relapse.
- Time to death: calculated from date of study registration to date of death due to any cause. Patients last known to be alive are censored at date of last contact.

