13.0 Statistical Considerations

13.1 Analysis of Primary Objective

Since this is a pilot study, several descriptive analyses will be performed. These will include examining the change in each measure of cardiotoxicity from the initial pre-chemotherapy assessment to each of the available post-chemotherapy imaging assessment (i.e. EF, LVEDV, LVESV, T1/T2 mapping, myocardial strain). These comparisons will be made using paired T-tests. Similar analyses will be performed using the ECHO-derived measures. In addition to examining the continuous changes in measures, we will determine the proportion of patients who exhibit a cardio-toxic event at 3-months defined as have a reduction in LVEF \geq 10% and EF \leq 50% when compared to baseline. This event will be defined for both the ECHO and MRI measures. In addition to point estimates of these rates, 95% confidence intervals will be calculated.

Additional toxicity measures will be tabulated after each visit.

CYTARABINE PLUS CONTINUOUS INFUSION DAUNORUBICIN, WITH CARDIAC
MRI MONITORING, INDUCTION THERAPY FOR ADULTS WITH ACUTE MYELOID
LEUKEMIA; A FEASIBILITY STUDY

Wake Forest Baptist Comprehensive Cancer Center (WFBCCC) CCCWFU 22616

For feasibility assessment, we will determine the proportion of patients with study-related deviations and report these proportions with 95% confidence intervals. In addition, we will determine the proportion of patients who complete the infusion therapy.

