13.2 Analysis of Secondary Objective

Similar toxicity analyses as described above for the primary objective will be examined at the 6-month time point.

We will report frequencies of response status (Overall response rate [CR + CRI]; Induction death rate; Percentage of patients with persistent leukemia; Disease-free survival [for those who achieve remission]) with the number of patients in each category of response. Treatment outcomes will be stratified by age (≥ 60 , < 60), ECOG (0-2, 3), cytogenetic risk groups and prior hematological disease (e.g. MDS, MPN).

Three sets of correlation analyses will be performed; the first will determine the correlation between ECHO and MRI assessments performed pre-chemotherapy; the second will assess correlations between post-chemotherapy ECHO and MRI assessments; and the third will assess correlations between each of the time points. In addition to the correlation analyses, paired t-tests will be performed to compare the actual values of each ECHO/MRI measurement to each other at each time point. Finally, Bland-Altman plots will be generated at baseline, follow-up and using the change in measure for each of the MRI/ECHO derived measures.

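### Primary outcome 5.1.2 (unexpected grade 3 or higher toxicity) is only tabulated after each visit: section 13.1 gives it no per-patient proportion, no confidence interval and no counting rule

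*Combined protocol and SAP*

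**What the plan says.** Section 5.1 lists three primary outcomes: cardiac toxicity (5.1.1), toxicity of the kind "Other unexpected toxicities (exclude hematologic and infectious" at CTCAE grade 3 or higher (5.1.2), and feasibility (5.1.3). Outcome 5.1.2 has no stated unit of analysis and no time window. The 3-month horizon comes from objective 2.1.1.

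Section 13.1 treats the three differently:

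- **5.1.1:** "we will determine the proportion of patients who exhibit a cardio-toxic event at 3-months", and then "In addition to point estimates of these rates, 95% confidence intervals will be calculated".
- **5.1.3:** "we will determine the proportion of patients with study-related deviations and report these proportions with 95% confidence intervals".
- **5.1.2:** "Additional toxicity measures will be tabulated after each visit". This is the only sentence that covers it.

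Section 8.2 supplies a natural denominator, "All patients will be evaluable for toxicity from the time of their first treatment with daunorubicin", but no analysis of 5.1.2 uses it. For the later time point, section 13.2 refers back to 13.1 and adds no method: "Similar toxicity analyses as described above for the primary objective will be examined at the 6-month time point". The precision statement in section 13.3 concerns the 3-month cardio-toxicity rate only.

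**The concern.** Objective 2.1.1 asks whether the continuous-infusion regimen is safe at 3 months. Among the primary outcomes, 5.1.2 is the one that looks for serious harm beyond the cardiac definition. A tabulation with no stated numerator, denominator or counting rule does not answer that question in patients.

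Two analysts could follow 13.1 faithfully and report different things: one a cumulative list of affected patients, the other a set of counts by visit. The second kind of count depends on how long a toxicity lasts and how often a patient is assessed. Adverse-event evaluation recurs through the section 6.0 schedule, so the difference could show.

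The missing interval matters separately. With about 40 patients, a table with few or no entries can read as reassurance although it excludes little.

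**Working it through.** **Does another sentence already give 5.1.2 a rate or an interval?** No.

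- The interval sentence in 13.1 comes before the tabulation sentence, and the rates it refers to are the ECHO and MRI cardio-toxic event rates just defined.
- The second interval in 13.1 belongs to protocol deviations.
- Section 8.2 defines who is evaluable, not what is estimated.
- Sections 13.2 and 13.3 add nothing for this outcome.

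**Inputs.** Section 13.3 gives 40 enrolled, up to 20% loss by 3 months, 32 evaluable, and exact Clopper-Pearson 95% limits. The documents give no expected rate for 5.1.2, so the event counts below are assumptions.

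**The plan's own figures first.** 32 / (1 − 0.20) = 40. The exact interval for 16 of 32 is 0.3189 to 0.6811, so the half-width is (0.6811 − 0.3189) / 2 = 0.181. This matches section 13.3.

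**The same method applied to 5.1.2.** For x patients with an event out of n:

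- lower limit = the 0.025 quantile of Beta(x, n − x + 1)
- upper limit = the 0.975 quantile of Beta(x + 1, n − x)
- for x = 0, the upper limit reduces to 1 − 0.025^(1/n)

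So 0/40 gives 1 − 0.025^(1/40) = 8.8%, and 0/32 gives 1 − 0.025^(1/32) = 10.9%.

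| Patients with an event (assumed) | n = 40 treated | n = 32 observed |
|---|---|---|
| 0 | 0% (0 to 8.8%) | 0% (0 to 10.9%) |
| 2 | 5% (0.6 to 16.9%) | 6.25% (0.8 to 20.8%) |
| 4 | 10% (2.8 to 23.7%) | 12.5% (3.5 to 29.0%) |

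**Why two denominators.** Not every treated patient need be under adverse-event observation at 3 months.

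- Section 13.3 allows up to 20% loss.
- Section 6.1 takes patients without remission after two inductions off study.
- Section 6.6 guarantees adverse-event monitoring only for 30 days after the last study drug.

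As an illustration, assume re-induction starts on day 15, straight after the 14-day first cycle, and no further drug is given. The last cytarabine day is then 15 + 4 = 19, and guaranteed monitoring ends at day 19 + 30 = 49. That falls short of 3 months counted from first dose. Dividing by all treated patients would count such a patient as event-free without having observed it.

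**What the counting rule can change.** Suppose 4 of 40 patients each have one toxicity present at 3 evaluations (assumed numbers). A count by visit gives 4 × 3 = 12 entries. A count by patient gives 4/40 = 10% (2.8 to 23.7%). The text fits either.

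**The case against.** Section 13.1 calls this a pilot study with descriptive analyses. No hypothesis, threshold or go/no-go rule depends on a 5.1.2 rate, and the outcome is narrow: only unexpected toxicities, with hematologic and infectious ones excluded. Tabulation is a recognisable choice for such events. Section 9.4 and Appendix C also send unexpected grade 4 and all grade 5 events to individual committee review.

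This limits the weight of the point but does not remove it. The same descriptive section commits to intervals for the other two primary outcomes, and committee review yields no rate and does not cover grade 3.

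Three stronger readings are tempting and are not supported:

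- **That a lasting toxicity is recounted at every visit.** The sentence in 13.1 may give only the timing of the tabulation, for example a cumulative table that is updated. Recounting is neither required nor excluded.
- **That affected patients cannot be told apart.** The adverse event log in Appendix F carries a patient identifier and is headed by cycle. What is unspecified is the summary, so the gap can be closed at analysis.
- **That the response outcomes in section 13.2 share the fault because they are given as frequencies.** That section also promises the number of patients in each response category, so intervals can be computed. Printing them is a separate preference.

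**Conclusion.** The point stands as a modest omission. For one of its three primary outcomes, the plan states no patient-level estimate and no uncertainty, although it provides both for the other two and already defines a usable denominator.

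The size is best seen at zero events, where the data would still be compatible with a true rate of up to 8.8% with 40 patients or 10.9% with 32. The figure of 32 assumes that the loss rate in section 13.3 carries over to adverse-event observation, which the documents do not say. The 12-entry example shows only that the readings differ, not that the trial would report 12.

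Nothing here affects the sample size or the power figures, and the point does not show that the reported toxicity would be wrong. It shows that the plan leaves open how the toxicity would be counted and leaves its precision unstated.

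**What to change.** In section 13.1, replace the tabulation sentence with text to this effect:

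- Report the number and proportion of patients treated with daunorubicin (the section 8.2 set) who have at least one 5.1.2 toxicity from first daunorubicin dose to the 3-month assessment. Count each patient once, at worst grade, and give an exact 95% confidence interval.
- Report how many patients without an event left adverse-event observation before 3 months. Repeat the proportion and interval among patients observed to 3 months or to an event.
- Keep the visit tables as supportive.

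The repeat is needed because the all-treated proportion treats unobserved time as event-free, which can understate the rate. Dropping event-free leavers tends to overstate it. If leaving is unrelated to the risk of a later toxicity, the two proportions should bracket the answer apart from sampling error.

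The cost is a few sentences and a little more programming, provided the log records events by patient with dates and grades. No extra patients, visits or tests are needed. The one drawback is presentational: a table with no events will carry an upper bound that looks less favourable than an empty table.

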5.2 Secondary Outcomes

- 5.2.1 Cardiac toxicity(see 2.2.2), as measured by MRI (ejection fraction [EF], left ventricular end diastolic volume [LVEDV], left ventricular end systolic volume [LVESV], T1/T2 mapping and myocardial strain) measures and ECHO (EF, myocardial strain, LVEDV, LVESV, ESV, mitral inflow E, A, E' and A') measures. Cardiac toxicity is defined as reduction in LVEF of $\geq 10\%$ compared to baseline LVEF and $EF \leq 50\%$ on the follow-up scan. This assessment will be performed using both an ECHO and MRI measure. In addition, these secondary outcomes will be assessed at the 6 month follow-up (or relapse) visit
- 5.2.2 Treatment outcomes (such as overall response rate) stratified by age (≥ 60 , < 60) and ECOG (0-2, 3): Overall response rate (CR + CRI); Induction death rate; Presence of persistent leukemia; Disease-free survival (for those who achieve remission)
- 5.2.3 Measures of ECHO and MRI derived measures of EF, myocardial strain, LVEDV and LVESV.

CYTARABINE PLUS CONTINUOUS INFUSION DAUNORUBICIN, WITH CARDIAC MRI MONITORING, INDUCTION
THERAPY FOR ADULTS WITH ACUTE MYELOID LEUKEMIA; A FEASIBILITY STUDY
 Wake Forest Baptist Comprehensive Cancer Center (WFBCCC) CCCWFU 22616

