6.6 Duration of Follow Up

Patients will have an MRI without contrast and full/limited ECHO at 3 months or relapse, whichever occurs first. Patients still on protocol at 6 months post-treatment will have an MRI without contrast only.

Patients will be followed for a minimum of 30 days after the last study drug is administered or until death, whichever occurs first, for adverse events monitoring. Patients removed from the study for unacceptable adverse events will be followed until resolution or stabilization of the adverse event.

CYTARABINE PLUS CONTINUOUS INFUSION DAUNORUBICIN, WITH CARDIAC
MRI MONITORING, INDUCTION THERAPY FOR ADULTS WITH ACUTE MYELOID
LEUKEMIA; A FEASIBILITY STUDY

Wake Forest Baptist Comprehensive Cancer Center (WFBCCC) CCCWFU 22616

Patients will be followed by phone call every 3 months for monitoring survival endpoints.

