Appendix E: Cardiac Function Worksheet

Cardiac Function Worksheet

PID _____ Study Number _____ MRN _____ Continuous infusion completed? Y / N [#] #If No, Amount infused: _____ ml Duration: _____ hrs _____ min		Baseline (Pre- Induction)	*Prior to Induction Cycle 2 Date: _____ / _____ / _____	3 mo. follow-up or relapse 3 Mo. _____ Follow-up _____ Date: _____ / _____ / _____	6 mo. follow-up or relapse 6 Mo. _____ Follow-up _____ Date: _____ / _____ / _____
MRI		w/o contrast	NA	w/o contrast	w/o contrast
EF	%				
LVEDV	ml				
LVESV	ml				
Mean T1					
Mean T2					
Global longitudinal strain	%				
MRI Completed		Y / N	NA	Y / N	Y / N
Person recording information					
ECHO		Full 3D	Ltd w/ strain	Ltd w/ strain	NA
EF	%				
LVEDV	ml				
LVESV	ml				
Global longitudinal strain	%				
ESV	ml				
Mitral inflow E velocity					
Mitral inflow A velocity					
Mitral inflow A' velocity					
Mitral inflow E' velocity					
ECHO Completed		Y / N	Y / N	Y / N	NA
Person recording information					
Troponin Levels					
		Pre-Induction	Cycle 1/ Day 4	*Cycle 2/ Day 3	Notes
Levels		ng/ml	ng/ml	ng/ml	
Brand of troponin assay used#					
Person recording information					

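### The 6-month cardiac toxicity outcome requires an ECHO that is never scheduled, and the MRI–ECHO concordance objective has no analysis of agreement on the event

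*Combined protocol and SAP*

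**What the plan says.** **6-month event.** Section 5.2.1 defines cardiac toxicity as a fall in LVEF of at least 10% from baseline with a follow-up EF of 50% or less, and then states: "This assessment will be performed using both an ECHO and MRI measure. In addition, these secondary outcomes will be assessed at the 6 month" visit, or at relapse. Section 13.2 asks for toxicity analyses like those of 13.1 at 6 months. Section 13.1 says of the event: "This event will be defined for both the ECHO and MRI measures".

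**Imaging schedule.** Section 6.6 provides for the first follow-up: "Patients will have an MRI without contrast and full/limited ECHO at 3 months or relapse, whichever occurs first". For the later one it says: "Patients still on protocol at 6 months post-treatment will have an MRI without contrast only". The task lists in 8.2 match this. The ECHO list reads "ECHO (at pre-induction visit, *post-treatment (pre-discharge), 3 month follow-up or relapse" and stops there, while the MRI list reads "MRI (at pre-induction visit, 3 month follow-up or relapse, at 6 month follow-up or relapse". In the Appendix E worksheet, the column headed "6 mo. follow-up or relapse" has entries for MRI, but ECHO is marked not applicable for both the scan type and the completion box.

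**Concordance.** Objective 2.2.3 is to compare how well MRI and ECHO concur in identifying cardiac toxicity, and it restates the two-part event rule. The related outcome, 5.2.3, lists the continuous measures from both modalities. Section 13.2 plans correlations, paired t-tests and Bland-Altman plots of those measures. Section 13.1 plans a separate event proportion with a 95% confidence interval for each modality.

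**The concern.** There are two gaps, both on secondary endpoints.

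First, a defined outcome has no data source. An analyst following 5.2.1 and 13.2 would have to report a 6-month ECHO event rate, and nobody is scheduled for the scan. The likely improvisations are to carry the 3-month ECHO forward, to use whatever unscheduled ECHOs exist, or to drop the result without comment. Each gives a different answer, and the plan chooses none of them.

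Second, the analysis does not match the objective. Concordance in identifying an event concerns the classification of individual patients. Two event rates can be equal while the modalities flag different people. A correlation can be high despite a systematic offset, and a paired t-test compares means. The trial could therefore report on 2.2.3 without saying how many patients would be called toxic by one method and not the other.

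**Working it through.** **Part (a): is there any route to a 6-month ECHO event?**

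| Source | ECHO at 6 months | MRI at 6 months |
|---|---|---|
| 5.2.1 (outcome) | required | required |
| 13.2 via 13.1 (analysis) | required for the event | required |
| 6.6 (follow-up) | no | yes |
| 8.2 (task list) | not listed | listed |
| Appendix E (worksheet) | not applicable | yes |

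The schedule table in section 6.0 is consistent with this: across the follow-up columns ECHO is marked once and MRI twice.

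Two phrases might seem to close the gap.

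- *The relapse alternative.* Under 6.6 there is one follow-up ECHO, at 3 months or relapse, whichever is earlier. A patient who relapses after 3 months has already had it. Only a patient who relapses before 3 months has a relapse ECHO.
- *Availability.* Section 13.1 applies the change analyses to "each of the available post-chemotherapy imaging assessment". At 6 months those analyses can run on MRI alone. The wording does not create an ECHO reading from which to derive the event.

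Scheduled 6-month ECHO scans: 0.

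**Part (b): what do the planned summaries leave undetermined?**

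Inputs from section 13.3: 40 enrolled, up to 20% drop-out, so 40 × 0.80 = 32 evaluable. The plan's precision figure reproduces: the exact Clopper-Pearson interval for 16/32 is 0.319 to 0.681, a half-width of 0.181. None of the figures in 13.3 is in dispute.

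The documents give no expected event rate, so the counts below are assumptions. Let each modality flag m of 32 patients, with a flagged by both. Then:

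- discordant patients = 2(m − a)
- overall agreement = (32 − 2(m − a))/32
- positive agreement = a/m
- negative agreement = (32 − 2m + a)/(32 − m)

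With m = 5, section 13.1 reports 5/32 = 15.6% (95% CI 5.3% to 32.8%) for both modalities in every row:

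| Shared (a) | Both / MRI only / ECHO only / neither | Discordant | Overall agreement (exact 95% CI) | Positive | Negative |
|---|---|---|---|---|---|
| 5 | 5 / 0 / 0 / 27 | 0 | 100% (89.1% to 100%) | 100% | 100% |
| 4 | 4 / 1 / 1 / 26 | 2 | 93.8% (79.2% to 99.2%) | 80% | 96% |
| 3 | 3 / 2 / 2 / 25 | 4 | 87.5% (71.0% to 96.5%) | 60% | 93% |
| 2 | 2 / 3 / 3 / 24 | 6 | 81.3% (63.6% to 92.8%) | 40% | 89% |

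With m = 3, both rates are 3/32 = 9.4% (95% CI 2.0% to 25.0%). Sharing 3, 2 or 1 patients gives 0, 2 or 4 discordant and positive agreement of 100%, 67% or 33%.

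The event rates planned in 13.1 are the same in every row, and the rows differ in exactly what 2.2.3 asks about.

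**The case against.** On part (a), 5.2.1 repeats 5.1.1 almost unchanged apart from the time point, so this may be a copying slip. The operational sections agree with one another, so sites would not be misled. Section 13.2 asks for similar, not identical, analyses. The 3-month primary outcome is unaffected, because both modalities are scheduled then. All of this is fair and limits the consequence, but the secondary outcome as written still cannot be produced in full.

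On part (b), this is a descriptive pilot, and 2.2.3 carries no hypothesis or threshold. Bland-Altman plots of EF and of change in EF do show agreement on the two quantities in the event rule, and with few events they may be more informative than a sparse table. Each patient's event status by each modality will exist, so a cross-tabulation could be added later. The illustration also uses equal event counts, the case that hides disagreement best; unequal rates would reveal some of it. And 32 is the evaluable number, while the number with complete pairs of scans could be smaller.

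These points make (b) an incomplete specification rather than an invalid method. They do not supply the missing count: no planned analysis applies the joint rule to both modalities in the same patient, and a 2x2 table is itself descriptive.

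**Conclusion.** Both parts hold. The 6-month ECHO event rate called for by 5.2.1 and 13.2 has no scheduled scan behind it, and the passages contradict each other. Objective 2.2.3 concerns agreement on a yes/no event, and the plan contains no analysis of that agreement. In the illustration, identical 15.6% event rates are compatible with anything from 0 to 6 discordant patients among 32 over the overlaps shown. That range rests on assumed event counts, equal rates in the two modalities and 32 complete pairs; the absence of the analysis rests on the text alone. The change should be made, but the 3-month primary outcome, the sample size and the stated power are not affected.

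**What to change.** 1. Reconcile 5.2.1 and 13.2 with 6.6, 8.2 and Appendix E. Which was intended is for the sponsor to state. If the imaging schedule stands, say in 5.2.1 and 13.2 that the 6-month event and change analyses use MRI only, and that MRI–ECHO comparisons are limited to baseline and 3 months (or relapse).
2. In 13.2, name as the analysis for 2.2.3 the paired 2x2 table of MRI event by ECHO event at 3 months (or relapse), in patients with both scans at both baseline and follow-up. Apply one event definition to both modalities, and state whether the 10% fall means EF points or a relative reduction.
3. Report the four cell counts, the number of patients without a complete pair, and the discordant proportion and overall agreement with exact 95% intervals. Give positive and negative agreement as descriptive point estimates. Keep the Bland-Altman plots as supporting evidence, and do not present correlation as agreement.

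If the imaging schedule stands, the cost is a few sentences and one table from scans already scheduled, with no change to the sample size. The drawback is imprecision: 28/32 agreement, for example, has an interval of 71.0% to 96.5%, and positive agreement would carry no interval.
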